#### 8.1.2. Secondary Efficacy Assessments

##### 8.1.2.1. Patient-Reported Outcomes

###### 8.1.2.1.1. *Functional Outcomes of Sleep Questionnaire (FOSQ)*

The FOSQ will be included to assess change in FOSQ domains and total score from baseline to Week 52. The FOSQ is a 30-item sleep-specific, participant-completed questionnaire used to assess the effect of disorders associated with excessive daytime sleepiness (EDS) on daily functioning in adults. It assesses the following 5 domains of

- General productivity (8 items)
- Activity level (9 items)
- Vigilance (7 items)
- Social outcomes (2 items)
- Intimate and sexual relationships (4 items)

The FOSQ items assess participant's current status with each item rated on a scale of 1 (extreme difficulty) to 4 (no difficulty), with an additional not applicable (0 = "I don't do this activity for

other reasons”) also available. Individual domain scores are calculated by taking the mean of answered, non-zero items within each domain and a total score can be calculated by first computing the mean score for each domain, then multiplying the mean of the domain scores by 5 (Weaver et al. 1997). The total score for the FOSQ 10-item short form (FOSQ-10) can also be calculated.

#### ***8.1.2.1.2. PROMIS Short Form v1.0 Sleep-related Impairment 8a***

The PROMIS Short Form v1.0 Sleep-related Impairment 8a assesses self-reported perceptions of alertness, sleepiness, and tiredness during usual waking hours, and the perceived functional impairments associated with sleep problems or impaired alertness. The PROMIS Short Form v1.0 Sleep-related Impairment 8a consists of 8 items each rated on a 5-point scale ranging from “not at all” to “very much.” Items have a recall period of “in the past 7 days.” Individual item scores are totaled to obtain a raw score, with higher scores indicating more sleep-related impairment. Raw scores can be converted to a T-score, which is standardized with a mean of 50 and a SD of 10. (Northwestern, 2016a)

#### ***8.1.2.1.3. PROMIS Short Form v1.0 Sleep Disturbance 8b***

The PROMIS Short Form v1.0 Sleep Disturbance 8b assesses self-reported perceptions of sleep quality, sleep depth, and restoration associated with sleep, including perceived difficulties and concerns with getting to sleep or staying asleep, as well as perceptions of the adequacy of and satisfaction with sleep. The PROMIS Short Form v1.0 Sleep Disturbance 8b consists of 8 items each rated on a 5-point scale ranging from “not at all” to “very much,” “never” to “always,” or “very poor” to “very good.” Items have a recall period of “in the past 7 days.” Individual item scores are totaled to obtain a raw score, with higher scores indicating more sleep disturbance. Raw scores can be converted to a T-score, which is standardized with a mean of 50 and a SD of 10. (Northwestern, 2016b)

#### ***8.1.2.1.4. Epworth Sleepiness Scale***

The ESS will be included to assess improvements in excessive daytime sleepiness from baseline to Week 52. The ESS is an 8-item participant-completed measure that asks the participant to rate on a scale of 0 (would never doze) to 3 (high chance of dozing), their usual chances of dozing in 8 different daytime situations, with a recall period of “in recent times.” The ESS total score is the sum of the 8-item scores and ranges from 0 to 24, with higher scores indicating greater daytime sleepiness (Johns 1991).

#### ***8.1.2.1.5. Short-Form 36 Version 2 Health Survey, Acute Form, 1-week Recall Version***

The SF-36v2 will be included to assess health-related quality of life from baseline to Week 52. The SF-36v2 acute form, 1-week recall version is a 36-item generic, participant-completed measure designed to assess the following 8 domains over “the past week.”

- Physical functioning
- Role-physical
- Bodily pain
- General health
- Vitality
- Social functioning

- Role-emotional, and
- Mental health

The Physical Functioning domain assesses limitations due to health “now” while the remaining domains assess functioning “in the past week.” Each domain is scored individually and information from these 8 domains are further aggregated into 2 health component summary scores: Physical Component Summary and Mental Component Summary. Items are answered on Likert scales of varying lengths (3-point, 5-point, or 6-point scales). Scoring of each domain and both summary scores are norm based and presented in the form of T-scores, with a mean of 50 and SD of 10; higher scores indicate better levels of function and/or better health (Maruish 2011).

#### **8.1.2.1.6. *Patient Global Impression of Status – Obstructive Sleep Apnea (PGIS-OSA) Symptoms Scales***

Three patient global impression of status scales will be included to assess categorical shift in participant self-rated assessment of their OSA symptom severity from baseline to Week 52.

##### **PGIS-OSA Fatigue**

This is a single-item, participant self-rated assessment of their overall level of fatigue due to OSA, “over the past 7 days.” The item is rated on a 4-point scale ranging from “No fatigue” to “Severe fatigue.”

##### **PGIS-OSA Sleepiness**

This is a single-item, participant self-rated assessment of their overall level of sleepiness due to OSA during waking hours, “over the past 7 days.” The item is rated on a 4-point scale ranging from “Not at all sleepy” to “Very sleepy.”

##### **PGIS-OSA Snoring**

The PGIS-OSA Snoring scale consists of two items. The first item is a participant self-rated assessment of their overall perception of the severity of their snoring due to OSA, “over the past 7 days,” with respect to how much their snoring has affected their sleep. The item is rated on a 4-point scale ranging from “Not at all affected” to “Very affected.” For the second item, participants will be asked on a 3-point scale (“Not at all” to “All the time”) if they have ever been told by someone else that they snore in their sleep.

### **8.1.3. Exploratory Efficacy Assessments**

#### **8.1.3.1. Actigraphy**

The actigraphy device (AX6) will be utilized in the OSA trial to objectively evaluate the effect of tirzepatide on various sleep and physical activity parameters including but not limited to change of daytime sleep time, sleep efficiency, and change in daytime physical activity from baseline. The actigraphy device is a data logger capable of recording raw data from a suite of integrated sensors and can be configured to collect movement-relevant data in an uninterrupted fashion for up to 2 months, thus is ideal for collecting longitudinal movement data (for example, physical activity, sleep, etc.) in real-world health research and well-defined clinical trials. The actigraphy device meets the CE (Conformite Europeenne) mark requirements. Participants should wear the actigraphy device for 7 consecutive days, 5 times during the study, per the SoA.

Lack of participation in actigraphy collections at any time is not considered a protocol deviation.

### **8.1.3.2. Patient Global Impression of Change – Obstructive Sleep Apnea (PGIC-OSA) Symptoms Scales**

Four patient global impression of change scales will be included to assess categorical shift in participant self-rated assessment of change in their OSA symptom severity from baseline to Week 52.

#### **PGIC-OSA Fatigue**

This is a single-item, participant self-rated assessment of the change in their overall level of fatigue due to OSA, “since you started taking the study medication.” The item is rated on a 5-point scale ranging from “Much worse” to “Much better.”

#### **PGIC-OSA Sleepiness**

This is a single-item, participant self-rated assessment of the change in their overall level of sleepiness due to OSA during waking hours, “since you started taking the study medication.” The item is rated on a 5-point scale ranging from “Much more sleepy” to “Much less sleepy.”

#### **PGIC-OSA Sleep Quality**

This is a single-item, participant self-rated assessment of the change in their overall sleep quality due to OSA, “since you started taking the study medication.” The item is rated on a 5-point scale ranging from “Much worse” to “Much better.”

#### **PGIC-OSA Snoring**

This is a single-item, participant self-rated assessment of the overall change in how their snoring has affected their sleep, “since you started taking the study medication.” The item is rated on a 5-point scale ranging from “My sleep is much more affected” to “My sleep is much less affected.”

### **8.1.3.3. EQ-5D-5L**

The EQ-5D-5L (EuroQol Research Foundation 2019) is a standardized 5-item self-administered instrument for use as a measure of health outcome. It provides a simple descriptive profile and a single index value for health status that can be used in the clinical and economic evaluation of health care as well as population health surveys. The EQ-5D-5L assesses 5 dimensions of health:

- mobility
- selfcare
- usual activities
- pain/discomfort, and
- anxiety/depression.

The 5L version, scores each dimension at 5 levels:

- no problems
- slight problems
- moderate problems
- severe problems, and
- unable to perform/extreme problems.

A total of 3125 health states is possible. In addition to the health profile, a single health state index value can be derived based on a formula that attaches weights to each of the levels in each dimension. This index value ranges between less than 0 (where 0 is a health state equivalent to death; negative values are valued as worse than dead) to 1 (perfect health). In addition, the EQ Visual Analog Scale records the respondent's self-rated health status on a vertical graduated (0 to 100) visual analog scale. The participant rates his/her perceived health from 0 (the worst imaginable health) to 100 (the best imaginable health). In conjunction with the health state data, it provides a composite picture of the respondent's health status.

## **8.2. Safety Assessments**

Planned time points for all safety assessments are provided in the SoA.

### **8.2.1. Physical Examinations**

A complete physical examination will include, at a minimum, assessments of the CV, respiratory, gastrointestinal and neurological systems as well as a thyroid examination. Height, weight, and waist circumference will also be measured and recorded.

A symptom-directed physical assessment will be performed as indicated in the SoA, as clinically indicated.

Investigators should pay special attention to clinical signs related to previous serious illnesses.

### **8.2.2. Vital Signs**

For each participant, vital signs measurements should be conducted according to the SoA (Section 1.3).

### **8.2.3. Electrocardiograms (ECG)**

Single 12-lead ECG will be obtained as outlined in the SoA (see Section 1.3) using an ECG machine that automatically calculates the heart rate and measures PR, QRS, QT, and QTc intervals.

A local single 12-lead ECG will be collected at designated visits. ECGs should be collected prior to collection of blood samples for laboratory testing, including PK samples. Participants should be supine for at least 5 minutes before ECG collections and remain supine but awake during the ECG collection. ECGs may be repeated at the investigator's discretion at any visit.

After enrollment, if a clinically significant increase in the QT/QTc interval from baseline or other clinically significant quantitative or qualitative change from baseline is identified, the participant will be assessed by the investigator for symptoms (for example, palpitations, near syncope, and syncope) and to determine whether the participant can continue in the study. The investigator or qualified designee is responsible for determining if any change in participant management is needed and must document his/her review of the ECG printed at the time of evaluation from at least 1 of the replicate ECGs from each time point.

### **8.2.4. Clinical Safety Laboratory Tests**

See Section 10.2, Appendix 2 for the list of clinical laboratory tests to be performed and the SoA for the timing and frequency.

The investigator must review the laboratory results, document this review, and report any clinically relevant changes occurring during the study as an AE. The laboratory results must be retained with source documents unless a Source Document Agreement or comparable document cites an electronic location that accommodates the expected retention duration. Clinically significant abnormal laboratory findings are those which are not associated with the underlying disease, unless judged by the investigator to be more severe than expected for the participant's condition.

All laboratory tests with values considered clinically significantly abnormal during participation in the study should be repeated until the values return to normal or baseline or are no longer considered clinically significant by the investigator or medical monitor.

- If such values do not return to normal/baseline within a period of time judged reasonable by the investigator, the etiology should be identified and the sponsor notified.
- All protocol-required laboratory assessments, as defined in Section 10.2, Appendix 2 must be conducted in accordance with the SoA, standard collection requirements, and laboratory manual.

If laboratory values from non-protocol specified laboratory assessments performed at an investigator-designated local laboratory require a change in participant management or are considered clinically significant by the investigator (for example, SAE or AE or dose modification), then report the information as an AE.

### **8.2.5. Pregnancy Testing**

See the SoA (Section 1.3) for testing for pregnancy and timepoints.

See Appendix 4 (Section 10.4) for additional information for pregnancy.

### **8.2.6. Suicidal Ideation and Behavior Risk Monitoring**

Patients with obesity may occasionally develop suicidal ideation or behavior.

Participants should be monitored appropriately and observed closely for SIB or any other unusual changes in behavior, especially at the beginning and end of the course of intervention, or at the time of dose changes, either increases or decreases. Participants who experience signs of SIB should undergo a risk assessment. All factors contributing to SIB should be evaluated and consideration should be given to discontinuation of the study intervention.

Baseline assessment of suicidal ideation and behavior/intervention emergent suicidal ideation and behavior will be monitored using the C-SSRS and PHQ-9.

#### **8.2.6.1. C-SSRS**

Columbia Suicide-Severity Rating Scale (C-SSRS) is a scale that captures the occurrence, severity, and frequency of suicidal ideation and behavior during the assessment period via a questionnaire. The scale was developed by the National Institute of Mental Health (NIMH) trial group (TASA) for the purpose of being counterpart to the Columbia Classification Algorithm of Suicide Assessment (C-CASA) categorization of suicidal events. (The Columbia Lighthouse Project, 2013)

For this study, the C-SSRS is adapted for the assessment of the ideation and behavior categories only. The Intensity of Ideation and Lethality of Behavior sections are removed.

### 8.2.6.2. PHQ-9

The PHQ-9 is a validated self-report screening tool that assesses the presence and intensity of depressive symptoms. The PHQ-9, which incorporates the 9 Diagnostic and Statistical Manual-IV depression criteria as “0” (not at all) to “3” (nearly every day), was developed for use in primary care settings (Kroenke et al. 2001).

## 8.3. Adverse Events, Serious Adverse Events, and Product Complaints

The definitions of the following events can be found in Section 10.3, Appendix 3:

- AEs
- SAEs
- PCs

These events will be reported by the participant (or, when appropriate, by a caregiver, surrogate, or the participant’s legally authorized representative).

The investigator and any qualified designees are responsible for detecting, documenting, and recording events that meet these definitions and remain responsible for following up events that are serious, considered related to the study intervention or study procedures, or that caused the participant to discontinue the study intervention before completing the study (see Section 7).

Care will be taken not to introduce bias when detecting events. Open-ended and non-leading verbal questioning of the participant is the preferred method to inquire about event occurrences.

After the initial report, the investigator is required to proactively follow each participant at subsequent visits/contacts. All SAEs and AEs of special interest (as defined in Section 8.3.3) will be followed until resolution, stabilization, the event is otherwise explained, or the participant is lost to follow-up (as defined in Section 7.3). For PCs, the investigator is responsible for ensuring that follow-up includes any supplemental investigations as indicated to elucidate the nature and/or causality. Further information on follow-up procedures is provided in Section 10.3, Appendix 3.

### 8.3.1. Timing and Mechanism for Collecting Events

This table describes the timing, deadlines, and mechanism for collecting events.

Event	Collection Start	Collection Stop	Timing for Reporting to Sponsor or Designee	Mechanism for Reporting	Back-Up Method of Reporting
AE					
AE	Signing of the ICF	participation in study has ended	As soon as possible upon site awareness	AE CRF	N/A

Event	Collection Start	Collection Stop	Timing for Reporting to Sponsor or Designee	Mechanism for Reporting	Back-Up Method of Reporting
SAE					
SAE and SAE updates – prior to start of study intervention and deemed reasonably possibly related to study procedures	Signing of the ICF	start of intervention	Within 24 hours of awareness	SAE CRF	SAE paper form
SAE and SAE updates – after start of study intervention	Start of intervention	participation in study has ended	Within 24 hours of awareness	SAE CRF	SAE paper form
SAE a – after participant's study participation has ended and the investigator becomes aware	After participant's study participation has ended	N/A	Promptly	SAE paper form	N/A
Pregnancy					
Pregnancy in female participants and female partners of male participants	After the start of study intervention	until 1 month after the last dose of study intervention	Within 24 hours (see Section 8.3.2)	Pregnancy paper form	Pregnancy paper form
PCs					
PC associated with an SAE or might have led to an SAE	Start of study intervention	End of study intervention	Within 24 hours of awareness	PC form	N/A

Event	Collection Start	Collection Stop	Timing for Reporting to Sponsor or Designee	Mechanism for Reporting	Back-Up Method of Reporting
PC not associated with an SAE	Start of study intervention	End of study intervention	Within 1 business day of awareness	PC form	N/A
Updated PC information	—	—	As soon as possible upon site awareness	Originally completed PC form with all changes signed and dated by the investigator	N/A
PC (if investigator becomes aware)	Participation in study has ended	N/A	Promptly	PC form	

Abbreviations: AE = adverse event; CRF = case report form; ICF = informed consent form; N/A = not applicable; PC = product complaint; SAE = serious adverse event.

a Serious adverse events should not be reported unless the investigator deems them to be possibly related to study treatment or study participation.

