### 8.3.2. Pregnancy

#### Collection of pregnancy information

##### Male participants with partners who become pregnant

- The investigator will attempt to collect pregnancy information on any male participant's female partner who becomes pregnant while the male participant is in this study. This applies only to male participants who receive study intervention.
- After learning of a pregnancy in the female partner of a study participant, the investigator will
  - obtain a consent to release information from the pregnant female partner directly, and
  - within 24 hours after obtaining this consent will record pregnancy information on the appropriate form and submit it to the sponsor.

- The female partner will also be followed to determine the outcome of the pregnancy. Information on the status of the mother and child will be forwarded to the sponsor. Generally, the follow-up will be no longer than 6 to 8 weeks following the estimated delivery date. Any termination of the pregnancy will be reported regardless of gestational age, fetal status (presence or absence of anomalies) or indication for the procedure.

*Female participants who become pregnant*

- The investigator will collect pregnancy information on any female participant who becomes pregnant while participating in this study. The initial information will be recorded on the appropriate form and submitted to the sponsor within 24 hours of learning of a participant's pregnancy.
- The participant will be followed to determine the outcome of the pregnancy. The investigator will collect follow-up information on the participant and the neonate and the information will be forwarded to the sponsor. Generally, follow-up will not be required for longer than 6 to 8 weeks beyond the estimated delivery date. Any termination of pregnancy will be reported, regardless of gestational age, fetal status (presence or absence of anomalies) or indication for the procedure.
- While pregnancy itself is not considered to be an AE or SAE, any pregnancy complication or elective termination of a pregnancy for medical reasons will be reported as an AE or SAE.
- A spontaneous abortion (occurring at <20 weeks gestational age) or still birth (occurring at  $\geq 20$  weeks gestational age) is always considered to be an SAE and will be reported as such.

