### 10.4.2. Contraception Guidance

#### 10.4.2.1. Females

**WOCBP who are completely abstinent as their preferred and usual lifestyle, or in a same sex relationship, as part of their preferred and usual lifestyle**

Must...	Must not...

 
• agree to either remain abstinent, or
 
• stay in a same sex relationship without sexual relationships with males
 
	
 
• use periodic abstinence methods 
 
◦ calendar
 
◦ ovulation
 
◦ symptothermal, or
 
◦ post-ovulation
 
 
 
• declare abstinence just for the duration of a trial, or
 
• use the withdrawal method
 

**WOCBP who are NOT completely abstinent as their preferred and usual lifestyle, or in a same sex relationship, as part of their preferred and usual lifestyle**

Topic	Condition
Pregnancy testing	Negative serum result at screening, followed by a negative urine result within 24 hours prior to treatment exposure.
Contraception	Agree to use 2 forms of effective contraception, where at least one form must be highly effective (less than 1% failure rate) for the duration of the trial and for 30 days thereafter.

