#### 10.4.2.2. Males

The table below describes contraception guidance for all men.

Topic	Guidance
For all men	should refrain from sperm donation for the duration of the study and for 120 days (4 months) from the last dose of study intervention received
Contraception for men with partners of childbearing potential	
 
● either remain abstinent (if this is their preferred and usual lifestyle), or
 
● must use condoms during intercourse for the duration of the study, and
 
● for 120 days (4 months) from the last dose of study intervention received
 

Contraception for men in exclusively same sex relationships, as their preferred and usual lifestyle	Are not required to use contraception

Examples of highly effective, effective and unacceptable methods of contraception are listed in Section 10.4.2.1, Appendix 4.

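### The protocol gives three different end points for pregnancy reporting and contraception; for men who complete treatment, partner pregnancies in about 85 to 92 of the 120 post-dose contraception days fall outside both collection rules

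*Protocol*

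**What the plan says.** Three parts of the protocol set a window.

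- **Section 8.3.1 (event collection table).** A single row, "Pregnancy in female participants and female partners of male participants", starts once study intervention begins and runs "until 1 month after the last dose of study intervention". The reporting-time cell of that row points to Section 8.3.2.
- **Section 8.3.2 (Pregnancy).** The investigator tries to collect information on a partner "who becomes pregnant while the male participant is in this study", and collects it on "any female participant who becomes pregnant while participating in this study". After the study, the only provision is for pregnancy-related SAEs that the investigator judges reasonably related to study intervention. It is listed under female participants, and the investigator need not look for such events.
- **Appendix 4 (Section 10.4.2).** Men with partners of childbearing potential, unless abstinent, "must use condoms during intercourse for the duration of the study" and also "for 120 days (4 months) from the last dose of study intervention received". Women of childbearing potential who are not abstinent use contraception "for the duration of the trial and for 30 days thereafter".

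Section 7.1 keeps participants who stop study intervention in the study for the remaining visits. The Schedule of Activities continues urine pregnancy tests at Weeks 12, 24, 36 and 52.

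**The concern.** The sponsor set contraception windows that run past the end of the study, but neither collection rule runs as long. A partner who conceives on day 60 after a completer's last dose is inside the 120-day window. She is outside the 8.3.1 table and, because the man has left the study, outside 8.3.2 as well. The post-study SAE provision does not mention partners.

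Sites also have two stop dates for anyone who stops drug early and stays in follow-up: one section says collection has closed while the other still requires a report.

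What is at stake is safety information. Pregnancy outcomes are rare in a trial of this size and are hard to recover once sites treat collection as closed.

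**Working it through.** **Inputs.** Screening 4 weeks, treatment 52 weeks, follow-up 4 weeks (Section 4.1); the collection and contraception windows above. Assumptions: a month is 30 days (28 to 31 tried), and the last weekly dose of a completer falls at Week 51 or Week 52. Days count from randomization.

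**The plan's own figure.** 4 + 52 + 4 = 60 weeks, as stated. Study end is therefore about Week 52 + 4 = 56, or day 56 × 7 = 392.

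**Completers.** A pregnancy is collected if either rule covers it, so the gap runs from the later of the two collection stops to the end of the contraception window.

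| | Last dose Week 51 | Last dose Week 52 |
|---|---|---|
| Last dose | day 357 | day 364 |
| 8.3.1 stop (last dose + 30) | day 387 | day 394 |
| 8.3.2 stop (study end) | day 392 | day 392 |
| Later stop | day 392 | day 394 |
| Male contraception end (last dose + 120) | day 477 | day 484 |
| Partner days uncovered | 477 − 392 = 85 | 484 − 394 = 90 |
| Share of the 120 days | 85/120 = 71% | 90/120 = 75% |
| Share of the full male window | 85/477 = 17.8% | 90/484 = 18.6% |
| Female contraception end (392 + 30) | day 422 | day 422 |
| Female days uncovered | 422 − 392 = 30 | 422 − 394 = 28 |

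Month length changes little. With a Week 52 last dose and a 28-day month, 8.3.1 stops at day 392. The partner gap is then 484 − 392 = 92 days (77% of 120; 92/484 = 19.0%) and the female gap is 30. With a 31-day month the stop is day 395 and the gaps are 89 and 27. Overall: 85 to 92 days for partners and 27 to 30 days for women.

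**Early stoppers who stay in the study.**

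| Last dose | 8.3.1 stop | 8.3.2 stop | Days in conflict | Last dose + 120 | Post-dose partner days outside both |
|---|---|---|---|---|---|
| Week 8 (day 56) | day 86 | day 392 | 306 | day 176 | 0 |
| Week 12 (day 84) | day 114 | day 392 | 278 | day 204 | 0 |
| Week 48 (day 336) | day 366 | day 392 | 26 | day 456 | 456 − 392 = 64 |

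A man whose last dose is on or before day 392 − 120 = 272 (272/7 = 38.9 weeks) and who stays to study end has all 120 days covered by Section 8.3.2. For women who stay to study end, the 30 days after it remain uncovered whenever they stopped drug.

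**The case against.** The strongest reply is that nothing in the protocol says reporting must last as long as contraception. Appendix 4 is contraception guidance; it does not define an exposure or risk window. No objective in Section 3 concerns pregnancy outcomes. For women, one month of collection after the last dose is about as long as a 30-day tail; the mismatch arises because Appendix 4 counts from trial end. The 8.3.1 row also refers to 8.3.2, so a careful site may read the two together, and follow-up of a known pregnancy continues after the participant leaves the study. These points stand, and they limit the weight of the finding.

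They do not remove it. The cross-reference leads to a different stop date, with no rule for which prevails, and no text gives a route for a partner pregnancy after the study.

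Three stronger readings are tempting but unsupported:

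- *Most of the male window is never captured.* The 71 to 77% applies only to the 120 post-dose days of completers. Appendix 4 also covers the whole study, where partner pregnancies are collected, and on that basis the uncovered share is about 18 to 19%. Men who stop early and stay can be fully covered.
- *A woman who stops drug at Week 8 has about 44 weeks of uncollected pregnancies* (306/7 = 43.7). That is a conflict between two sections. Section 8.3.2 still requires the report, and scheduled urine tests continue.
- *Some 288 men are affected* (0.70 × 412). That is the approximate enrollment cap on all men. With 1:1 randomization about half, 144, would receive tirzepatide, and only non-abstinent men with partners of childbearing potential come under the condom rule. The documents give no expected number of pregnancies.

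**Conclusion.** The point holds as a safety-reporting inconsistency with a limited gap. For men who complete treatment, partner pregnancies in about 85 to 92 of the 120 post-dose days are outside both collection rules. For women who complete, the gap is about 30 days after study end. For early stoppers who remain in the study, Sections 8.3.1 and 8.3.2 contradict each other on when collection ends, but 8.3.2 still captures pregnancies up to study end.

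The figures rest on a last dose at Week 51 or 52, study end at Week 56 and a month of 28 to 31 days; no choice within those ranges changes the conclusion. Few events are likely. Type I error, power, sample size and the efficacy analyses are not affected. The correction is worth making because it is cheap and the missing reports could not easily be recovered later.

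**What to change.** Reconcile Sections 8.3.1, 8.3.2 and 10.4.2 so that the reporting window is never shorter than either study participation or the protocol's own contraception window:

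- partners of male participants: until the later of study end or 120 days after the last dose;
- female participants: until 30 days after study end.

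Split the pregnancy row in 8.3.1 accordingly, use the same wording in 8.3.2, and add a reminder at Visit 801 to report pregnancies within the window.

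The phrase *the later of* matters. A plain stop at 120 days after the last dose would end collection at day 176 (about Week 25) for a man who stops drug at Week 8, where Section 8.3.2 now runs to day 392. That would lose 216 days, about 31 weeks.

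No contraception or treatment rule changes. The cost is protocol wording, a reminder at an existing visit, and a few extra passive pregnancy reports and outcome follow-ups after study end.
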